Oral suspension (mL) bid	2.0	2.5	3.0	3.5	4.0	5.0	5.5	6.0	7.0
Reduced Dose (mg) bid	13.3	16.7	20	23.3	26.7	33.3	36.7	40	46.7
Oral suspension (mL) bid	1.3	1.7	2.0	2.3	2.7	3.3	3.7	4	4.7

In addition, in case a subject will have a consistent (e.g., at least 2 consecutive evaluations) platelets count  $\leq 150 \times 10^9/L$  and not meeting the stopping criteria for platelets, the Investigator will have to reduce the dose of 1/3 of the current dose.

Moreover, for subjects who have already reduced the dose of 1/3 an additional reduction by 20% is allowed for safety reasons.

For **all subjects**, during the first month of treatment, platelets count assessment will be performed weekly, while during the second month it will be performed every 2 weeks, in order to strictly monitor this parameter for safety reasons.

If the dose is reduced due to platelet count  $\leq 150 \times 10^9/L$ , and/or white blood cell  $< 3.0 \times 10^9/L$  and/or hemoglobin  $< 10.0 \text{ mg/dL}$ , a complete blood count (i.e.CBC) test must be performed weekly for 8 consecutive weeks.

	Any decision relevant to the dose adjustment and/or modification of schedule of assessments can be discussed with the Medical Monitor, but the final decision remains with the Investigator only or its authorized designee
Other:	As the subjects to be randomised are on stable steroids, the recommended national immunisation schedule, including varicella immunity, should be completed (i.e., as recommended in the “Diagnosis and Management of Duchenne muscular dystrophy” DMD guideline  ), before the Screening Visit. However, in case of live or live attenuated vaccines to be administered during the study, the Investigator can discuss, but it is not mandatory, the case with the Medical Monitor of the study and must carefully monitor the subject.
Independent Data Monitoring Committee:	An independent Data Monitoring Committee (IDMC) will review, evaluate and categorise safety findings every 3 months during the study and will be responsible for oversight of the formal interim analysis (see below). The IDMC will have access to unblinded data, if necessary, and will operate according to the rules defined in the IDMC charter.

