**For subjects randomized under protocol version 4.0:**

Study drug can be reduced by 1/3 of the starting dose at which the AE leading to temporary stop occurred, once platelets and/or white blood cell and/or hemoglobin are normalized and/or triglycerides return to levels below 300 mg/dL (3.42 mmol/L), or diarrhoea is mild. The subject may have more than the usual number of scheduled visits if needed, until the AE resolves, and then will continue the study as per scheduled visits.

If a subject was randomized with baseline triglycerides above 300 mg/dL (3.42 mmol/L) the Investigator can discuss how to manage the case with the medical monitor, however the final decision remains with the Investigator only or its authorized designee.

In addition, in case a subject will have a consistent (e.g., at least two consecutive evaluations) platelets count  $\leq 150 \times 10^9/L$  and not meeting the stopping criteria for platelets, the Investigator will have to reduce the dose by 1/3 vs the starting dose (see Section 8.2.2 for more details).

If a subject has a medical event not necessarily drug related that requires interruption of study drug dosing for >4 weeks, the Investigator can discuss the case with the medical monitor if the subject may resume study drug treatment, however the final decision remains with the Investigator only or its authorized designee.

Moreover, for subjects who have already reduced the dose of 1/3 an additional reduction of 20% is allowed for safety reasons following the instruction in section "*For subjects randomized under protocol version 6.0, or 7.0 or 8.0*".

Any decision relevant to the dose interruption and/or modification of the schedule of assessments can be discussed with the Medical Monitor, but the final decision remains with the Investigator only or its authorized designee.

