**Table 2: Placebo or Givinostat Starting Dose**

Weight (kg)	≥10 and < 12.5	≥12.5 and < 20	≥20 and < 25	≥25 and < 30	≥30 and < 40	≥40 and < 50	≥50 and < 60	≥60 and < 70	≥70
Dose (mg) bid	13.3	16.7	20	23.3	26.7	33.3	36.7	40	46.7
Oral suspension (mL) bid	1.3	1.7	2.0	2.3	2.7	3.3	3.7	4	4.7

The subjects who were randomized under protocol version 4.0 will continue the current dose (see Table 4).

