**Table 4: Placebo or Givinostat Dose Modification for subjects randomized under study protocol version 6.0 or 7.0 or 8.0.**

Weight (kg)	$\geq 10$ and $< 12.5$	$\geq 12.5$ and $< 20$	$\geq 20$ and $< 25$	$\geq 25$ and $< 30$	$\geq 30$ and $< 40$	$\geq 40$ and $< 50$	$\geq 50$ and $< 60$	$\geq 60$ and $< 70$	$\geq 70$
Starting Dose (mg) bid	13.3	16.7	20	23.3	26.7	33.3	36.7	40	46.7
Oral suspension (mL) bid	1.3	1.7	2.0	2.3	2.7	3.3	3.7	4	4.7
Reduced Dose (mg) bid	10.6	13.4	16	18.6	21.4	26.6	29.4	32	37.4
Oral suspension (mL) bid	1.1	1.3	1.6	1.9	2.1	2.7	2.9	3.2	3.7

Study drug can be resumed at a level 20% smaller than the dose at which the AE leading to temporary stop occurred, once platelets and/or white blood cell and/or hemoglobin are normalized and/or triglycerides return to levels below 300 mg/dL (3.42 mmol/L) or when diarrhoea is mild.

For subjects randomized under protocol version 6.0 or 7.0 or 8.0, only one dose reduction is allowed during the treatment period.

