**Table 5: Placebo or Givinostat Dose Modification for subject randomized under study protocol version 4.0**

Weight (kg)	≥10 and <12.5	≥12.5 and <20	≥20 and <25	≥25 and <30	≥30 and <40	≥40 and <50	≥50 and <60	≥60 and < 70	≥70
Starting Dose (mg) bid	20	25	30	35	40	50	55	60	70
Oral suspension (mL) bid	2.0	2.5	3.0	3.5	4.0	5.0	5.5	6.0	7.0
Reduced Dose (mg) bid	13.3	16.7	20	23.3	26.7	33.3	36.7	40	46.7
Oral suspension (mL) bid	1.3	1.7	2.0	2.3	2.7	3.3	3.7	4	4.7

Study drug dose adjustment including safety rules for permanently or temporarily stopping study drug are described in Section 7.3.1.

As mentioned in Section 7.3.1, in case a subject has a consistent (e.g., at least 2 consecutive evaluations) platelets count  $\leq 150 \times 10^9/L$  and does not meet the stopping criteria due to platelet reduction, the Investigator will have to reduce the dose by 1/3 of the starting dose (see Table 5).

Study drug can be resumed at a level 1/3 smaller than the dose at which the AE leading to temporary stop occurred, once platelets and/or white blood cell and/or hemoglobin are normalized and/or triglycerides return to levels below 300 mg/dL (3.42 mmol/L) or when diarrhoea is mild.

If a subject was randomized with baseline triglycerides above 300 mg/dL (3.42 mmol/L), the Investigator can discuss how to manage the case with the medical monitor, however the final decision remain with the Investigator or its authorized designee only.

Moreover, for subjects who have already reduced the dose of 1/3 an additional reduction by 20% is allowed for safety reasons following the instruction reported in Table 4.

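### For boys randomised under version 4.0, the protocol gives conflicting rules for a second platelet-driven dose reduction, and one note points them to another cohort's dose table

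*Protocol*

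**What the plan says.** Three places in the protocol set the dose change for a version 4.0 boy whose platelets are at or below 150 x 10^9/L on consecutive tests but who does not meet a stopping criterion:

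- Synopsis, Dose adjustment: "the Investigator will have to reduce the dose of 1/3 of the current dose".
- Section 7.3.1: "the Investigator will have to reduce the dose by 1/3 vs the starting dose".
- Section 8.2.2, text under Table 5: "the Investigator will have to reduce the dose by 1/3 of the starting dose".

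All three are worded as obligations. Each place also permits, for safety reasons, a further 20% cut in a boy who has already come down by a third. Section 7.3.1 sends that step to the instructions for versions 6.0 to 8.0, and section 8.2.2 sends it to Table 4. The synopsis gives it no reference.

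The restart rule after a temporary stop also varies. Section 7.3.1 says "Study drug can be reduced by 1/3 of the starting dose at which the AE leading to temporary stop occurred". Section 8.2.2 says "Study drug can be resumed at a level 1/3 smaller than the dose at which the AE leading to temporary stop occurred", and the synopsis agrees with 8.2.2.

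On the continuing dose, the note under Table 2 says that version 4.0 boys "will continue the current dose (see Table 4". Table 4 is headed "Dose Modification for subjects randomized under study protocol version 6.0 or 7.0 or 8.0". The version 4.0 starting and reduced doses are in Tables 3 and 5.

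**The concern.** The trigger and the cohort are the same in all three places, but the reference dose is not. That matters as soon as the current dose differs from the starting dose.

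This state was common. Section 8.2.1 reports that, by 18 June 2018, approximately 50 to 60% of randomised subjects with at least 8 weeks of treatment had already reduced the starting dose because of platelets (blinded data). A limit of one reduction is stated in 7.3.1 and 8.2.2 for versions 6.0 to 8.0. No sentence says that the one-third rule for version 4.0 applies only once.

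The dose decision rests with the investigator, and section 8.2.2 makes discussion with the Medical Monitor optional, so two sites could treat the same situation differently while each follows the text. At stake is consistent handling of a safety signal. A dose also cannot be judged a protocol deviation, under SAP sections 2.10 and 3.2, unless one rule governs it.

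**Working it through.** **Inputs.** Version 4.0 starting doses are from Table 3. Reduced doses are from Table 5, which matches the one-third table in the synopsis. The 20% step is from Table 4.

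**1. Reproduce the protocol's figures.** Starting dose x 2/3 gives 13.3, 16.7, 20, 23.3, 26.7, 33.3, 36.7, 40 and 46.7 mg bid, which are all nine Table 5 reduced doses. These are also the Table 4 starting doses. Multiplying them by 0.8 gives 10.6, 13.4, 16, 18.6, 21.4, 26.6, 29.4, 32 and 37.4 mg, which are all nine Table 4 reduced doses. The tables are internally correct.

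**2. First reduction.** Current dose = starting dose = s, so a third off the current dose is s x 2/3 and a third of starting removed is s - s/3. These are equal. The wordings agree in every band.

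**3. Weight loss before any reduction.** Section 8.2.2 moves such a boy to the Table 2 or Table 3 dose for his new weight and treats him as still on a starting dose. A boy moved from 40 to 35 mg then goes to 35 x 2/3 = 23.3 mg under either wording, which is the Table 5 entry for his new band. This takes starting dose to mean the tabulated dose for the new band.

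**4. A boy already reduced by a third, with platelets again persistently low.** Take c = 2s/3 as his current dose. The synopsis rule read literally gives c x 2/3. The 20% step gives c x 0.8.

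| Weight (kg) | Starting, mg bid | After one-third cut | Third off current | 20% step (Table 4) |
|---|---|---|---|---|
| 10 to <12.5 | 20 | 13.3 | 8.9 | 10.6 |
| 12.5 to <20 | 25 | 16.7 | 11.1 | 13.4 |
| 20 to <25 | 30 | 20 | 13.3 | 16 |
| 25 to <30 | 35 | 23.3 | 15.5 | 18.6 |
| 30 to <40 | 40 | 26.7 | 17.8 | 21.4 |
| 40 to <50 | 50 | 33.3 | 22.2 | 26.6 |
| 50 to <60 | 55 | 36.7 | 24.5 | 29.4 |
| 60 to <70 | 60 | 40 | 26.7 | 32 |
| 70 or more | 70 | 46.7 | 31.1 | 37.4 |

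In the 30 to <40 kg band the gap is 21.4 - 17.8 = 3.6 mg per dose, or 7.2 mg a day. Apart from rounding, the first figure is always (2/3)/0.8 = 0.833 of the second, that is, one sixth lower.

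**5. Restart after a temporary stop.** For a boy stopped while on his starting dose, the 7.3.1 wording and the 8.2.2 wording coincide. For a boy stopped at an already reduced dose, 8.2.2 and the synopsis still define a reference dose. The phrase in 7.3.1 does not describe him, because the event did not occur at his starting dose.

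**6. The pointer under Table 2.** Table 4 starting doses are two thirds of those in Table 3 in every band (26.7 against 40 mg at 30 to <40 kg). They match what a version 4.0 boy receives only if he has already had the one-third cut.

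**The case against.** The strongest reply is that the second reduction has its own rule. All three places carry a sentence for boys already reduced by a third. Section 7.3.1 routes it to instructions that contain the same platelet trigger and a 20% cut of the current dose, and Table 4 takes 26.7 to 21.4 mg. On this view 17.8 mg, which appears in no dosing table, comes only from applying the first-reduction sentence twice. Much of this stands: the 20% route is usable and specific. It does not remove the conflict. The 20% step is allowed while the one-third rule is required, the synopsis gives no routing, and no text confines the one-third rule to a first reduction.

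The pointer under Table 2 is also fairly described as a slip. Its own sentence says that the current dose continues, Table 3 follows directly, the later version 4.0 paragraph names Table 5, and the title of Table 4 names other versions. It remains a wrong reference in operative dosing text.

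Three stronger readings are tempting, and the documents do not support them:

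- A reader might infer four competing doses for the boy at 26.7 mg by adding 13.4 mg (a further 40/3 mg removed) and 26.7 mg unchanged. Both apply the starting-dose wording again to a boy who is already a third below his starting dose, and pass over the sentence written for his case.
- A reader might infer that the wordings diverge after weight loss. That needs starting dose to mean the randomisation dose, which the protocol does not say and which the weight-loss paragraph of 8.2.2 points away from.
- A reader might infer damage to the dose and exposure summaries. SAP section 3.4 summarises the dose administered, allowing for modifications. An unclear instruction may change which dose is given, but the summary still reports what was taken.

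**Conclusion.** The text is wrong as written, within a narrow scope. For version 4.0 boys, the synopsis and sections 7.3.1 and 8.2.2 name different reference doses for the same mandatory reduction. This has no effect at a first reduction. For a boy already reduced by a third, the text supports either a third off the current dose or the 20% step, and the first is one sixth lower than the second. The restart wording has the same fault, and the note under Table 2 cites the wrong cohort's table.

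Two things limit the practical size. The documents do not say how many version 4.0 boys were still on treatment under version 8.0, or how many had a second low-platelet episode. The 50 to 60% in section 8.2.1 counts reductions of the starting dose, not second reductions. Nothing here bears on alpha, power or the primary analysis. No view is taken on which dose or rule is right.

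**What to change.** Reconcile the synopsis, section 7.3.1 and section 8.2.2 for version 4.0 boys so that:

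- one reference dose is used for the low-platelet reduction, and one for restarting after a temporary stop;
- the term starting dose is defined, including after a weight-loss adjustment;
- the text states which rule governs a second reduction, and whether it is required or permitted.

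Correct the cross-reference in the note under Table 2. The sponsor must decide which rule is intended.

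The cost is protocol wording and a clarification letter to sites, with no change to the design or the analysis. The listing in SAP section 3.5 already flags subjects with more than one dose reduction. The sponsor can use it to count the boys affected and record which rule was applied, which is the main use of the clarification if few of them remain on treatment.

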#### Primary Efficacy Endpoint

The change in 4-stairs climb (4SC) from baseline to 18 months will be evaluated in the target population. The data will be analyzed using an Analysis of Covariance (ANCOVA) model with the change in 4SC from baseline to 18 months as the dependent variable and with terms for baseline 4SC value as a covariate and randomised treatment, concomitant steroid use and age at baseline as independent class variables. Least squares means (Lsmeans) will be estimated for givinostat and placebo. The treatment effect, being difference in Lsmeans, will be presented along with the associated 95% confidence interval and the p-value. Significance will be achieved if the 1-sided p-value is  $\leq 0.025$ .

#### Analysis of Key Secondary Endpoints

Formal analyses of functional secondary endpoints (i.e., cumulative loss of function in the NSAA, change in 6MWT, NSAA, time to rise from floor and muscle strength by knee extension and elbow flexion) and Vastus lateralis MFF will be performed in the target population at 18 months using the same approach as described for the primary endpoint. Possible need for log transformation of these variables will be assessed prior to unblinding by assessment of ANCOVA model residuals without a treatment effect term.

#### Safety Data

Safety data will be evaluated descriptively. All subjects (target and off-target population combined) who took at least 1 dose of study drug will be included in the summary of safety. The following parameters will be summarized: rates of discontinuation, AEs, and laboratory abnormalities. Adverse event data will be coded using the Medical Dictionary for Competent Activities (MedDRA). Summary statistics will be presented for changes in vital signs. Laboratory test values will be summarised similarly, but will also include tabulation of the number of subjects shifting from within the reference range at

	baseline to outside of the reference range on randomised treatment.
--	---

### 3 LIST OF ABBREVIATIONS

Abbreviation	Definition
4SC	4-stairs climb
6MWT	Six-minute walking test
ADR	Adverse drug reaction
AE	Adverse event
ALP	Alkaline phosphatase
ALT	Alanine aminotransferase
ANCOVA	Analysis of covariance
aPTT	Activated partial thromboplastin time
AST	Aspartate Aminotransferase
ATS	American Thoracic Society
AUC	Area under the curve
bid	twice daily
BMI	Body mass index
BUN	Blood urea nitrogen
CBC	Complete Blood Count
CFR	Code of Federal Regulations
C max	Maximum observed concentration
CRA	Clinical research associate
CRF	Case Report Form
CSA	Cross sectional area
CSOM	Clinical Study Operations Manual
CSR	Clinical study report
DAPC	Dystrophin-associated protein complex
DMD	Duchenne muscular dystrophy
DNA	Deoxyribonucleic acid
ECG	Electrocardiogram
ECHO	Echocardiogram
eCRF	electronic Case Report Form
EDC	Electronic Data Capture
EOS	End of study
EU	European Union
FAPs	Fibro-adipogenic progenitors
FDA	Food and Drug Administration

---

FEV1	Forced Expiratory Volume at 1 second
FVC	Forced Vital Capacity
GCP	Good Clinical Practice
GGT	Gamma-glutamyl transpeptidase
GI	Gastrointestinal
GSPV	Global Safety and Pharmacovigilance
Hct	Hematocrit
HDAC	Histone deacetylase
HDACi	Histone deacetylase inhibitors
HDL	High-Density Lipoprotein
HHM	Hand-held myometry
HIPPA	Health C Portability Accountability Act
IB	Investigator's Brochure
ICF	Informed Consent Form
ICH	International Conference on Harmonization
IDMC	Independent Data Monitoring Committee
IEC	Independent Ethics Committee
IL-1 $\beta$	Interleukin-1 beta
IND	Investigational New Drug
IRB	Institutional Review Board
IRT	Interactive response technology
ITT	Intention-to-Treat
LDH	Lactate dehydrogenase
LDL	Low-Density Lipoprotein
IFN- $\gamma$	Interferon gamma
IL-6	Interleukin-12
IL-12	Interleukin-6
LLN	Lower Limit Normal
Lsmeans	Least squares means
MCH	Mean corpuscular hemoglobin
MCHC	Mean corpuscular hemoglobin concentration
MCV	Mean corpuscular volume
MedDRA	Medical Dictionary for Competent Activities
MFAF	Muscle Fibers Area Fraction
MFF	Muscle fat fraction
MMT	Manual muscle testing

MoA	Mechanism of action
MRI	Magnetic resonance imaging
MRS	Magnetic resonance spectroscopy
mRNA	Messenger ribonucleic acid
nNOS	Neuronal nitric oxide synthase
NO	Nitric oxide
NOAEL	No-Adverse Effect Level
NSAA	North Star Ambulatory Assessment
OCT	Organic Cation Transporter 2
PEF	Peak Expiratory Flow
PI	Principal Investigator
PK	Pharmacokinetic
PODCI	Paediatric Outcomes Data Collection Instrument
PT	Prothrombin time
QT	QT interval
QTc	Corrected QT interval
QTcF	QT interval, Fridericia's correction
RBC	Red blood cell
ROM	Range of motion
SAE	Serious adverse event
SAP	Statistical Analysis Plan
SD	Standard deviation
TEAE	Treatment-emergent adverse event
TFT	Timed function test
TNF- $\alpha$	Tumor necrosis factor-alpha
TSA	Trichostatin A
ULN	Upper Limit Normal
US	United States
VL MFF	Vastus lateralis muscle fat fraction
WBC	White blood cell

## 4 INTRODUCTION

### 4.1 Background on Duchenne Muscular Dystrophy

Duchenne muscular dystrophy (DMD) is a rare degenerative, X-linked recessive genetic disorder with estimated incidence of 1 in 5000 live births (Mendell, J. R., et al.), caused by mutations in the dystrophin gene. In DMD, mutations in the dystrophin gene disrupt the open-reading frame, resulting in an absence of functional dystrophin, a critically important part of the protein complex that connects the cytoskeletal actin of a muscle fiber to the extracellular matrix.

Lack of dystrophin causes repetitive muscle damage. In a normal muscle, the physiological repair process removes the damaged muscle fibers and reconstitutes normal muscle fibers. In DMD, on the other hand, the repair process leads to a combination of new muscle fibers, fatty replacement and fibrosis, with the two latter components progressively prevailing as a process called fibroadipose degeneration. This detrimental outcome typically compromises muscle function, alters the tissue environment, and probably limits the potential effectiveness of regenerative approaches. As described by Peverelli et al., fibrosis is already significant at one year of age in DMD patients constituting approximately 16% of a muscle biopsy (3% in age matched controls) and remains relatively constant until 7 years of age. At this age, there is an important increase in the proportion of fibrosis that reaches approximately 30% of muscle biopsy between 7 and 10 years of age. Similarly MRI studies have shown that fat infiltration is already present at 5 years of age and constantly increases (Forbes, et al.).

Duchenne muscular dystrophy is characterized by progressive symmetrical muscular weakness that affects proximal muscles more than distal muscles, often accompanied by calf muscle pseudo hypertrophy.

Significant motor deficits may be present during the first year of life, but diagnosis is usually made between the ages of 3 to 5 years when the affected patients begin to show waddling gait, toe walking, and difficulty climbing stairs. Over time, ambulation becomes increasingly abnormal, and by 8 years of age, most patients lose the ability to rise from the floor and climb stairs, and often fall while walking. By 12 to 14 years of age, most lose the ability to walk and the heart and respiratory muscles also are affected. Upper limb, cardiac, and

diaphragmatic muscles progressively weaken during adolescence. After 18 years all patients are affected by cardiomyopathy. Only few survive beyond the third decade; most patients die because of respiratory complications and heart failure due to cardiomyopathy. There are still no curative treatments for such a debilitating disease and the current management of the disease is based on prevention and management of complications (Bushby, et al.).

Corticosteroids (e.g., prednisone or deflazacort) have been demonstrated to slow the rate of muscle weakness when initiated in ambulatory boys, however, the use of corticosteroids is limited by all the potential side effects, including weight gain, cataracts, osteopenia, and avascular necrosis (Manzur, A, et al.). Recently, the European Medicines Agency has granted a conditional approval to Ataluren, which targets nonsense mutations as the cause of DMD, which is relevant for only 13% of DMD population, or approximately 2,000 patients in the United States (US) and 2,500 patients in the European Union (EU).

In addition, FDA has granted an accelerated approval to Eteplirsen and Golodirsen, which targets DMD gene mutations skippable with exon 51 skipping and exon 53 skipping, respectively, which are relevant for only 21% of DMD population, or approximately 3,200 patients in the United States (US).

Ataluren, Eteplirsen and Golodirsen are the first of a number of treatments that are aimed at correcting the original genetic defect in the dystrophin gene.

Genetic Duchenne therapy via AAV Micro-dystrophin may be promising.

In light of the above considerations, it becomes evident that an unmet therapeutic need exists for the treatment of this disabling and fatal condition.

